As all visits are non-contact with the study worker staying at least 2m away at all times, the parent/carer will take the fingerprick sample for the child, using the same instructions as they use themselves (adolescents may take the sample themselves following the fingerprick guide) (see Section 9.6.1 below). The sampling kits for adults and children are identical, except that a paediatric lancet will be available for children who need it (adolescents may prefer to use the adult lancet depending on age and body size). Fingerprick samples will be processed using exactly the same methods and assay as for adult participants (see Section 9.9 below), and antibody results will be returned in the same way as for adult participants (see section 9.9.2 below). One important reason for using identical testing methods is to ensure comparability in antibody positivity results across the age range, rather than using a different test in those under 16 years from those 16 years and older. Use of identical methods and assays will mean the data are directly comparable. In contrast, saliva antibody tests used in the ONS Schools Infection Survey have an estimated sensitivity of only 80%¹⁶, meaning methods of analysis firstly need to make adjustments for this and secondly also need to account for different positivity thresholds. The minimum blood volume marked on the tube is 250µL, although the laboratory are able to process samples down to 200µL, but this provides a quantitative antibody level as well as a positive/negative result. This is essential moving forwards in the pandemic as it provides the flexibility to look at higher antibody levels which appear likely to be needed to neutralise different variants. This is also a major limitation of point of care lateral flow antibody tests, which do require smaller blood volumes, but each use their own

Clinical Research Protocol Template version 15.0

© Copyright: The University of Oxford and Oxford University Hospitals NHS Foundation Trust 2019 Page 47 of 113 individual threshold and again have much poorer sensitivity. For example the FORTRESS assay used in adults in the REACT study had sensitivity 84% and specificity 99% for PCR-confirmed cases/pre-pandemic sera (compared with >99% for the assay currently used in adults in the survey¹⁸), again leading to the same challenges with analysis as saliva based tests.

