The required reduction in sample size and transition to the new approach to delivery from 1 April 2022 will be achieved as follows. First, all participants will be informed that from 1 April 2022, the compensation vouchers will reduce from £25 to £20 per assessment, and that, if they prefer not to continue the study, they should contact the contact centre to withdraw. The numbers choosing to withdraw are unknown, but could be 5-25%. Depending on this, up to 20% of existing participants will be contacted in April 2022 to thank them for their participation and explain that the study has a reduced sample size and it will no longer be possible to continue to include them. Priority will be given to retaining participants with under-represented characteristics, including non-White ethnicity, higher deprivation, smaller household sizes, giving blood by fingerprick and with longest participation and fewest missed visits in the study wherever possible, to improve overall representativeness and maximise the value of the most complete histories of SARS-CoV-2 infections to meet objectives.

Remaining participants will be invited to transition to the new approach to delivery in four stages. Stages 2-4 form a randomised stepped wedge design, enabling statistical comparisons to be made between

answers to questionnaires administered by study workers or online/over the telephone, and swabs/bloods returned by different mechanisms, and ensuring that the study retains sufficient numbers under plausible assumptions to continue to report on positivity (see below).

- Stage 1 (target start date for opt in invitations 21 March 2022²) is a small scale transition of up to 2,000 households, sampled purposively to capture the experience of a range of ages, ethnicities, deprivation, household size and reported long-term health conditions, in transitioning to the new approach. All participants in Stage 1 will be asked to provide feedback on their experience of the new arrangements in order to improve logistics through short surveys; a purposively selected sub-sample will be invited to qualitative interviews (see Section 9.4.4.1 below for details). CDDO term this small scale initial transition the "private beta". CDDO approval is required to proceed to Stage 2.

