Assuming that 90% of participants respond to the initial communication, increasing to 99% after the 20-40 day reminder, that ultimately 81% of participants chose to transition to the new format (increasing gradually predominantly over the 6 weeks from the initial communication), that 90% respond in any given assessment window, that individual assessment window non-response is 10%, that overall 97% of sample kits posted that are returned are done so a median 7 days after the start of each assessment window, this staged approach would lead to the number of completed swab tests shown below in Figure 4 over weeks from start of Stage 2, assuming that a theoretical 100,000 participants are currently visited each week (approximately the case). If a greater percentage chose to continue in the study, then the final numbers will be higher, but the trends will be similar. As the percentages who will choose to continue are unknown, randomisation will be stratified, with households with under-represented characteristics, longest participation and fewest missed visits prioritised for randomisation in Stage 2 and 3, and other participants randomised across Stages 3 and 4. Depending on the percentage who agree to continue, some participants originally planned to be randomised to Stage 4 may need to be contacted to explain that it will no longer be possible to continue to include them, given the reduced sample size.

© Copyright: The University of Oxford and Oxford University Hospitals NHS Foundation Trust 2019 Page 52 of 113

² All dates are indicative targets, depending on approval from the Research Ethics Committee, completion of the database for online/telephone questionnaire completion, and, for later stages, approval from CDDO and absence of need to make other changes based on participant feedback.

Clinical Research Protocol Template version 15.0

During each of Stages 2, 3 and 4, adjusted estimates of swab and antibody positivity (adjusting for sex, age, ethnicity and region as used in the post-stratification (see Section 11.2), and also further adjusting for deprivation and household size) would be compared between those randomised to transition to the new approach to delivery and returning swab tests and those randomised to still receive study worker visits. This, together with analyses of response rates by these factors, will enable an assessment of whether future adjustments for response rates are necessary.

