((https://www.ukbiobank.ac.uk/media/zusjljce/ukb_serologystudy_report_month2_final-1.pdf)). From February 2021 to March 2022, all blood samples will also be tested for antibodies against the N (nucleocapsid) protein, rather than just the S protein, on the same sample as part of the single automated workflow. This should enable antibody responses to be categorised as against S only (compatible with vaccination) or against S and N (compatible with natural infection). Because anti-S is common to protection from both vaccination and natural infection, anti-S results will be returned to participants, but anti-N will not (this N-antibody test is currently for research uses only). From protocol v16.0, N-antibody will not be assayed on all samples due to capacity, but may be assayed in a subset determined either by random sampling, sampling according to date, or in specific groups of participants to test for missed infections. S-antibody results will be returned as positive or negative at the standard threshold used to identify those previously infected with SARS-CoV-2 vs not (based on plasma from prepandemic blood donors) as described above, in line with the MHRA CE marking for the test. However, this standard antibody threshold (42 ng/mL) was determined prior to vaccines being developed. This corresponds to 23.5 binding antibody units (BAU)/ml using the World Health Organization's (WHO) standardised units enabling comparison across different antibody assays. Currently, >97% of individuals are positive at this threshold²², meaning the vast majority get a positive result returned. A recent study

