In addition, the proportion of individuals with symptomatic and asymptomatic infection (based on PCR of nose and throat swabs) based on the latest result in the last two weeks will be summarised approximately every calendar week from the start of the study, overall and by geographical region. Proportions will be calculated incorporating sampling weights for the original ONS and NISRA surveys, this survey and for non-response to this survey, with 95% confidence intervals estimated using the Korn-Grauberd method which allows for the low anticipated positivity rates. We will use Bayesian methods in sensitivity analyses assessing the impact of plausible ranges of test sensitivity and specificity on results, incorporating both the assay performance and the fact that participants are self-swabbing. Associations between various predictors and ever testing positive for infection vs never testing positive will be estimated using unweighted proportions and Fisher's exact tests with multivariable logistic regression models to adjust for confounding. Factors considered will include sex, ethnicity, age at last birthday (as both categorical and continuous variables) and other responses to the short questionnaire. These factors will also be considered in multi-level regression models, similar to the main model over continuous time described above.

Similar spatiotemporal MRP methods will be used to estimate proportions over time with immunity defined based on the optical density readings from the ELISA assay for IgG antibodies versus the threshold defined in comparison with pre-pandemic plasma. We will also estimate the proportions with previous infection (as defined by antibodies) but no previous symptoms.

Random effects linear regression models will also be generated for the absolute optical density readings (potentially log-transformed depending on the distribution) in relation to time since onset of first symptoms, with those not reporting symptoms treated as an additional category (random effect per household – may be omitted depending on model fit). Additional factors considered in these models will include age, sex and ethnicity.

Incidence will be calculated indirectly by deconvoluting the Bayesian dynamic multi-level regression model estimate of swab positivity and an estimate of duration of PCR positivity based on those testing positive in the study. More details are provided on

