However, following maintenance of COVID-19 hospitalisation rates below levels that would overwhelm the NHS during the Omicron wave in December 2021-January 2022, and given ongoing infection rates above 3%, the need to maintain this level of precision around estimates of swab positivity has reduced. Therefore, as part of adapting to live with COVID-19, from April 2022 onwards, the swab targets will be reduced by ~25% and the blood targets by ~20% (i.e. retaining a greater percentage of those giving blood

in order to maintain as much precision as possible to monitor declines in antibodies, particularly in older age groups), to achieve the following:

- Swab target: up to ~227,300 swab samples taken from individuals 2 years and older every 28 days in England, ~15,650 in Wales, ~10,050 in Northern Ireland and ~23,200 in Scotland (~276,200 total across the UK every 28 days, ~300,000 swab samples in total across the UK per month)
- Blood target: up to ~90,850 blood samples taken from individuals 8 years and older every 28 days in England, ~6,300 in Wales, ~4,150 in Northern Ireland and ~9,200 in Scotland (~110,500 in total across the UK every 28 days, ~120,000 blood samples in total across the UK per month)

Reductions are proportionately less in Wales and Northern Ireland in order to maintain power within these countries, and proportionately more in England to meet the overall reductions. These numbers are considered to provide sufficient precision to monitoring infection rates and seroprevalence moving forwards, overall and by region/country, particularly given current levels of infection and antibody positivity. Targets are based on samples taken and arriving at the laboratories for testing rather than valid results received from the laboratories because assay failures also contribute to testing costs. Test failures with samples taken at study worker visits have generally been ~1% for swab tests and ~1.5% for blood tests; even if these increase with postal/courier return to 1-2% or 3-4% respectively, the sample targets above will retain reasonable precision. Test failure rates will be monitored closely, as will rates of samples that have been reported to have been taken failing to arrive at the consolidation hub (the latter are not included in the targets above).

[figure not shown]
Figure 5 Impact of sample size on precision for various estimates of prevalence

(a) With prevalence ranging from 0 to 10% on an absolute scale

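### The randomised comparison of delivery modes names only antibody positivity, which is near its ceiling at the standard cut; the measured concentration should be compared as well

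*Protocol*

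**What the plan says.** Protocol 9.4.4 makes transition Stages 2 to 4 a randomised stepped wedge and says the design allows comparison of "swabs/bloods returned by different mechanisms". The analysis it then names, for each of those stages, is a comparison of "adjusted estimates of swab and antibody positivity (adjusting for sex, age, ethnicity and region as used in the post-stratification", with further adjustment for deprivation and household size. The stated use is that, together with analyses of response rates, it "will enable an assessment of whether future adjustments for response rates are necessary".

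Section 9.4.4 does not restate the antibody cut. Section 11.2 defines the antibody outcome "versus the threshold defined in comparison with pre-pandemic plasma", and section 6 does the same. Section 9.6.1 says "this standard antibody threshold (42 ng/mL) was determined prior to vaccines being developed" and adds: "Currently, >97% of individuals are positive at this threshold". A second cut, 179 ng/mL, is used for returned results and for publication (9.6.1).

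The measured level is available. Section 9.9.1 has quantitative readings returned for the ELISA. Section 9.4.3 says of the laboratory test that "this provides a quantitative antibody level as well as a positive/negative result" and treats this as essential. Section 11.2 models absolute readings, but not by delivery mode. Section 11.3 explains that the blood target was cut less than the swab target "in order to maintain as much precision as possible to monitor declines in antibodies, particularly in older age groups".

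**The concern.** From v16.0 blood travels by priority post box or courier. Before that it was kept in a cool bag during the day and couriered to the laboratory, within 24 hours where possible (9.9.1). Once home visits stop there is no concurrent randomised control, so Stages 2 to 4 are the opportunity to learn whether the new route, or the people who respond to it, changes the antibody result.

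The only antibody outcome named for that comparison is a yes/no result that almost everyone passes. A proportional fall in measured level moves few people across 42 ng/mL, and a change confined to higher levels moves none. A fall linked to the switch would coincide with it in time and could be mistaken for part of the antibody decline that the blood cohort was retained to measure.

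**Working it through.** **1. The plan's own figures.** No power or precision figure is given for the transition comparison. The nearest antibody figures, in 11.3, reproduce:
- 50% against 55% with 1,800 per group, two-sided 5%: power 85.2% (stated 85%).
- Exact 95% interval width at 50%: 3.29% for n = 3,600 (stated below 3.3%) and 2.66% for n = 5,500 (stated below 2.7%).

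**2. Information kept by the cut.** For a uniform shift of a normal log concentration, the efficiency of a cut exceeded by a proportion p, relative to the mean, is φ(z_p)² / [p(1−p)].
- p = 0.97: z = 1.881, φ = 0.0680, so 0.0680² / (0.97 × 0.03) = 0.159, a loss of about 84%.
- p = 0.98: loss 88%. p = 0.99: loss 93%.
- Other shapes at 97%: logistic 90-91%, t with 10 or 5 df 89-92%, skewed shapes 42-92%.
- A cut that 70-90% exceed (an assumed range for 179 ng/mL; the protocol gives no figure): loss 42-66% under normality.

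**3. Stage 2, UK-wide.** From the protocol: 110,500 bloods per 28 days (11.3); 25% transitioned in Stage 2, 81% opt-in, 90% window response, 97% return (9.4.4).
- Transitioned: 110,500 × 0.25 × 0.81 × 0.90 × 0.97 = 19,534.
- Not yet transitioned: 110,500 × 0.75 = 82,875.
- Assumed: SD of ln concentration 1.0, household design effect 1.5, two-sided 5%.

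A fall of fraction f is a shift d = −ln(1−f)/SD. Positivity moves from 0.97 to Φ(1.881 − d). Both comparisons use z-tests with the variance multiplied by 1.5. The standard error on log concentration is √[1.5 × (1/19,534 + 1/82,875)] = 0.00974 SD.

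| Fall in level | d | Positivity | Power, positivity | Power, log concentration |
|---|---|---|---|---|
| 3% | 0.030 | 96.8% | 24% | 88% |
| 5% | 0.051 | 96.6% | 56% | >99% |
| 8% | 0.083 | 96.4% | 93% | >99% |
| 10% | 0.105 | 96.2% | 99% | >99% |
| 20% | 0.223 | 95.1% | >99% | >99% |

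Sensitivity to the SD: with 0.7, a 3% fall has power 43% against 99%. With 1.5, a 5% fall has 29% against 94%, and a 10% fall has 82% on positivity.

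**4. Stage 3.** With 60% invited (110,500 × 0.60 × 0.707 = 46,883) against 40% not yet invited (44,200), and the same assumptions, positivity has 73% power for a 5% fall at SD 1.0, and 94% for a 10% fall at SD 1.5.

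**5. A region-by-age group.** Section 11.3 gives about 2,000 results per month, under the earlier, larger blood target. The Stage 2 split gives 2,000 × 0.25 × 0.707 = 354 against 1,500. With SD 1.0 and no design effect, a 20% fall has power 33% on positivity and 97% on log concentration.

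**The case against.** The strongest reply is that the comparison is sound for its stated use. Section 9.4.4 uses it to judge adjustment for response rates, and the reported antibody outcome is itself a proportion positive (sections 6 and 11.2), so comparing that proportion is coherent. This stands: the named analysis is not invalid. It does not settle the matter, because the same section says the design allows comparison of bloods by return mechanism, and a near-ceiling outcome is also weak for showing whether responders differ in antibody level.

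The second reply is that large effects would not escape. A reader might infer that losing most of the information means a posting effect would be missed and read as waning. The table does not support that: UK-wide falls of about 8-10% or more are detected at SD 1.0, and the comparison is repeated in Stages 3 and 4. The documents also give no evidence that posting lowers the measured level; 9.9.1 reports that posted blood was tested successfully in another large study, which does not show that levels are unchanged.

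Third, the illustration is rough. The 110,500 is a target for samples reaching the laboratory, so multiplying by 0.707 may discount non-return twice. Without that factor (27,625 transitioned), positivity has 30% power for a 3% fall and 68% for 5%. The pattern is the same.

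A reader might also want swab CT values compared among positives. That conditions on the outcome, since weak samples that drop below detection leave the group, and CT is returned only where available. It is not proposed here.

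**Conclusion.** The point holds as a minor one. Section 9.4.4 names only positivity as the antibody outcome, and the cut the protocol defines for it is one that more than 97% exceed. Adding the measured level costs nothing in samples and fits the stated reason for keeping the blood cohort large.

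The exposure is limited to three things: small uniform shifts UK-wide (roughly 3-5% at SD 1.0), shifts within region-by-age groups, and changes at higher levels that do not cross 42 ng/mL. In addition, even a detected difference in positivity does not give the size of the shift: a 20% fall in level appears as 97.0% to 95.1%.

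The 16% efficiency is an approximation, not a protocol figure. It rests on a normal log concentration, a uniform shift, exactly 97% positive and the 42 ng/mL cut. The power figures also rest on the assumed SD and design effect. The protocol does not say how large a change in level would matter, so whether a 3-5% shift is important is open.

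**What to change.** In 9.4.4, add to the Stage 2-4 comparison the ratio of geometric mean anti-S concentration by delivery mode. Use the covariates already listed, plus each participant's last home-visit log concentration where available; this also helps separate who responds from what the return route does to the sample. Report the percentages above 42 and 179 ng/mL beside it. If the ratio differs materially from 1, consider a delivery-mode term in models of antibody level over time.

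Keep the positivity comparison for its use in response-rate adjustment. The cost is a few lines of protocol text and analysis code; the readings are already returned and no further samples are needed.

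### The Stage 2–4 comparison in Section 9.4.4 merges response selection with any effect of posted sampling, so its gap alone cannot show whether response adjustment is needed

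*Protocol*

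**What the plan says.** Protocol Section 9.4.4 moves existing participants from home visits to posted kits. Stages 2 to 4 are described as a randomised stepped wedge, and one purpose is to compare "swabs/bloods returned by different mechanisms".

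During each of these stages, adjusted swab and antibody positivity are compared between two groups: "those randomised to transition to the new approach to delivery and returning swab tests and those randomised to still receive study worker visits".

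The adjustment is described as "adjusting for sex, age, ethnicity and region as used in the post-stratification", with deprivation and household size added. The use of the result is then given: "This, together with analyses of response rates by these factors, will enable an assessment of whether future adjustments for response rates are necessary".

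Section 11.1 says that no formal statistical analysis plan exists, so Section 9.4.4 is where this comparison is defined.

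**The concern.** The question is whether people who respond under the new approach differ in positivity from those who do not, given the adjustment factors. The contrast chosen answers a different question. One side has been filtered by opting in and by posting back a swab. The other side has not been filtered in that way, and it was also sampled under a different mode, with a study worker present at a distance.

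The contrast equals zero when there is neither selection nor a mode effect, and also when the two offset each other. It differs from zero when either acts alone. Randomisation does not cure this, because the filter acts after randomisation.

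The comparison bears on how the prevalence series is carried across the change of mode in 2022. If a mode effect were read as selection, response weights would be added that cannot repair lower detection. If the two offset each other, selection within the adjusted strata could be missed while the comparison looked reassuring.

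**Working it through.** The protocol gives no sample size, power or threshold for this comparison, so there is no stated figure to reproduce.

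**Inputs from the protocol**

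- Section 9.4.4: 81% eventually opt in; 90% respond in a given window; 97% of kits returned (the wording is unclear and is read here as the share returned); Stage 2 moves 25%; a theoretical 100,000 participants visited per week, so 400,000 over about four weeks.
- Section 11.3: infection rates above 3%, so p = 0.03 as a round base.
- Lay summary: mean 2.1 participants per household, used as an upper bound on the design effect for clustering.
- Section 11.7: nominal 5% level.

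**Assumed, because the documents give no value:** the selection and mode effects, and 90% attendance at home visits.

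**Step 1. Share contributing a swab.** g = 0.81 × 0.90 × 0.97 = 0.707, so about 29% of the transition group is absent in a given window.

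**Step 2. What the contrast estimates.** Let r be true positivity in returners relative to everyone randomised, and s be detection by post relative to a home visit. Then observed ratio = r × s, and true positivity in non-returners = (p − g·p·r)/(1 − g).

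| r (selection) | s (mode) | New mode, observed | Home visit | Non-returners, true |
|---|---|---|---|---|
| 1.00 | 0.90 | 2.70% | 3.00% | 3.00% |
| 0.90 | 1.00 | 2.70% | 3.00% | 3.72% |
| 1.11 | 0.90 | 3.00% | 3.00% | 2.20% |

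For row 2: (0.03 − 0.707 × 0.027)/0.293 = 3.72%. Rows 1 and 2 look identical, yet only row 2 calls for response adjustment. Row 3 shows no gap although returners (3.33%) and non-returners (2.20%) differ.

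**Step 3. How visible a pure mode effect could be.** With r = 1, the chance that a 95% interval for the difference excludes zero is about Φ(|p₁ − p₀|/SE − 1.96), where SE² = D[p₁(1 − p₁)/n₁ + p₀(1 − p₀)/n₀], p₀ = 0.03, p₁ = 0.03s and D is the design effect.

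- *Full uptake within Stage 2 (upper end).* n₁ = 400,000 × 0.25 × 0.707 = 70,713 and n₀ = 400,000 × 0.75 × 0.90 = 270,000. For a 5% / 10% detection loss: 0.56 / 0.99 at D = 1, and 0.31 / 0.85 at D = 2.1.
- *Smaller base.* 450,275 active participants × 0.75 × 0.80 = 270,165, allowing for the upper withdrawal and removal figures in Section 9.4.4. For the same losses: 0.41 / 0.95 at D = 1, and 0.23 / 0.69 at D = 2.1.
- *Gradual uptake.* Section 9.4.4 expects opt-in to build up mainly over six weeks. Assume four weekly batches of 25,000, linear opt-in over 42 days and 7 to 16 days from opt-in to swab. That gives about 7,000 to 18,000 posted swabs by day 28. For the same losses: about 0.1–0.2 / 0.3–0.7 at D = 1, and about 0.1 / 0.2–0.4 at D = 2.1.

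**Step 4. Cancellation.** At the full-uptake sizes, a real +10% relative selection is visible with probability 0.98 if there is no mode effect, and 0.07 with a 10% detection loss (0.79 and 0.06 at D = 2.1).

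**The case against.** The best reply is that the contrast is one input to a judgement. Section 9.4.4 sets no test or trigger and pairs the contrast with response-rate analyses. Section 11.7 prefers confidence intervals to rigid thresholds. A reader might infer that a gap would automatically switch on response weights. The text does not say so, and the probabilities in the working only illustrate visibility. The response-rate analyses do not resolve the ambiguity, however. They show who responds by the listed factors, and cannot show whether responders differ in infection within those strata.

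Other parts of the reply also stand:

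- **Selection would not go wholly uncorrected.** Sections 11.2 and 11.8 apply post-stratification and weighting in any case. Only selection within the adjusted strata is exposed.
- **The mode comparison is not tied to this contrast.** A reader might infer that the aim of comparing return mechanisms rests on it. Section 9.4.4 assigns that aim to the stepped wedge as a whole, and participants' data before and after transition could support it.
- **Lower detection by post is not shown.** Section 11.3 allows for failure rates "even if these increase with postal/courier return to 1-2% or 3-4% respectively", but those are test failures. They give missing results, not false negatives. Both modes use swabs taken by the participant or parent, and Section 9.4.4 says that only the way they are delivered changes. Section 9.6.1 does let study workers explain and demonstrate the technique, so a zero effect is not assured.
- **The home-visit group is also selected to some degree.** Positivity is seen only in those who attend and give a swab.

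None of this separates the two effects within the contrast as written.

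**Conclusion.** The point holds as one of non-identification. The contrast returns selection times mode as a single quantity, and the protocol describes no analysis that separates them. The sensitivity analysis in Section 11.2 covers test performance and self-swabbing in general, not posted against home-visit sampling.

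Its practical size is unknown, because it depends on a mode effect for which the documents give no figure. With no mode effect the contrast is valid. With an assumed 5% to 10% detection loss and no selection, the chance of a visible gap in Stage 2 runs from about 0.1 to 0.99, depending on uptake, base size and clustering. The highest values need the full 81% opt-in within four weeks, which the protocol itself does not expect.

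A reader might conclude that the 2022 prevalence trend is biased. The documents do not support that. They support only that this gap, taken alone, cannot tell response bias from a change of mode.

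**What to change.** Keep the stated contrast as the real-time check and add two supplementary contrasts to Section 9.4.4. Both use the listed covariates plus length of participation and missed visits (which are used to prioritise staging), household-clustered standard errors and 95% confidence intervals.

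1. **Selection.** Within home-visit data from the same calendar weeks, including Stage 2 participants' own visits before transition, compare positivity between those who later opt in and return swabs and those invited who do not. Fix a cut-off for later opt-in, such as the final reminder, because Section 9.4.4 sets no time limit.
2. **Mode.** Compare new-mode returners with home-visit participants in the same weeks who later opt in and return swabs.

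Exclude, and report the number of, Stage 4 participants who are never invited, since their opt-in status is undefined. State that contrast 1 carries the main weight, though not the sole weight, in judging whether response adjustment is needed, and that the existing gap alone is not to be read as evidence of response bias.

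The cost is a change of wording and some extra analysis of data already held. The drawback is timing: the final reminder falls 60 to 80 days after invitation, so these results are complete only after later-stage opt-in is known and cannot fully inform decisions during each stage.
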